6.3 REMOVAL OF SUBJECTS FROM THE STUDY

All patients who are withdrawn from the study will still need to be monitored closely for 30 days for their safety. The following will be reasons to withdraw a participant from the study.

1. Participant request to be withdrawn from the study.
2. Safety concerns (adverse events or reactions etc.).
3. Investigator discretion (will usually be related to patient safety).
4. Treatment failure (the need for a longer parenteral therapy or hospital admission).

7 STUDY WORK FLOW

This is a prospective, open-label, two-phase study to evaluate the clinical utility of SQ administration of a novel furosemide formulation. Patients seen in the cardiology clinic who are determined to be eligible will be enrolled in this study.

For participants in the trial, during the clinic visit the study investigator, co-investigator who are physicians in the cardiology division of SEMC, or a cardiology nurse practitioner will teach the participants everything they need to know about the sc2Wear™ Furosemide Infusor.

scPharmaceuticals will conduct a training session for study staff on the device operation and placement and study site will have access to training materials developed by scPharmaceuticals.

The Pump will be filled and placed on the skin of the upper abdomen in accordance with the Instructions for Use Manual (Appendix C). The patient will be instructed on how to press the activator button to start the administration of the furosemide. When this button is pressed, a small needle is deployed automatically to the skin and the furosemide delivery starts. When the medicine has been delivered, the needle pulls back into the Cartridge and then the patient can then dispose of the cartridge. Participants will also be given Quick Reference Guide (QRG)(Appendix D) and will be given contact numbers from the cardiology department to call if any device troubleshooting questions come up. Participants will also be provided the technical support contact number related to the device.

8 Investigational Product

sc2Wear™ Furosemide Infusor delivery system comprises of reusable and disposable components. The components are described below.

(1) The reusable components which are needed for the drug delivery:

(a) The Activator consists of the electromotor and pump drive, control electronics, and user interface elements (buttons, visual indicators and audible tones),

(b) A Power Cord for recharging the Activator when not in use,

(2) The Disposable components:

(a) The drug product: Furosemide Injection Solution (8 mg/mL – total 80 mg in 10 mL), provided in a 10mL standard pharmaceutical glass vial,

(b) An Adapter for accessing the contents of the drug vial,

(c) A Cartridge that houses the needle and needle insertion mechanism, a micropiston pump, drug reservoir and adhesive (for attachment to the body),

(d) Cavilon No Sting Barrier Film - small wand applicator, 1.0 ml, One applicator wand, for protecting the skin.

(e) Alcohol Prep Pads for cleaning the top of the medicine Vial and the skin prior to applying the Pump.

(f) The device is adhered to the body using medical grade adhesive 1776 acrylate adhesive manufactured by 3M. The 1776 adhesive is identical to the commercially available 3M Mepitape [Class I, Exempt], except that a liner is added for converting/handling.

8.1 Buffered Furosemide Injection

Buffered furosemide injection (SCP-101, Furosemide Injection), 10mL of undiluted buffered furosemide solution (8 mg/mL), manufactured by Cook Pharmica, Bloomington, IN, USA under GMP conditions. Contains Tris Hydrochloride, Sodium Chloride and may contain Sodium Hydroxide and Hydrochloric acid for pH adjustment: pH 7.4 (7.0 - 7.8). The sc2Wear furosemide Infusor will be provided by scPharmaceuticals to the investigational site as a starter kit (containing the Activator, cartridge and drug) as well as refill kits containing the drug and cartridge.

8.2 Labeling

Study drug (Furosemide Injection Solution (SCP-101)) and study device (sc2WearTM Furosemide Infusor) will bear labels that meet applicable laws for an investigational drug-device combination, which may include, but is not limited to, the following information:

- Federal law statement
- Study/Investigator information
- Batch number

- Storage information

8.3 Storage and Handling

Store study drug at 20° - 25°C, (68° - 77°F), excursions permitted between 15°C and 30°C, (between 59°F and 86°F). Protect from Light. The sc2WearTM Furosemide Combination Product must be placed and activated within 7 hours of filling. Drug delivery must be started within 7 hours after filling the device.

9 STUDY EVALUATION

9.1 Baseline Evaluation

The following information will be obtained from patients who give informed consent.

- Age, sex, past medical history
- Physical examination
- Weight, height, Blood pressure, Heart Rate, Respiratory Rate, Temperature
- NYHA classification
- Laboratory draws (Sodium, potassium, chloride, Bun, Cr, Mg, pro-BNP, hemoglobin and hematocrit)
- Dyspnea Scale (Appendix B)
- Current medications

9.2 Study Days (3 ± 4 days)

During the study days, patients will be required to continue with their usual evening diuretic dose. The following information will be collected by the visiting nurse:

- Weight, Blood pressure, Heart Rate, Respiratory Rate, Temperature
- Physical exam
- Injection site inspection
- Blood draw (Sodium, potassium, chloride, bicarbonate, Bun, Creatine, and Mg)
- Current Medications
- Dyspnea scale (Appendix B)

- Electrolyte replacement
- Assessment for adverse events

9.3 Follow Up After Last Treatment

Subjects will be assessed in the office within 24 hours of termination of at home treatment.

Assessments will include:

- Weight, Blood pressure, Heart Rate, Respiratory Rate, Temperature
- Physical examination
- NYHA classification
- Injection site assessment
- Blood test (Sodium, chloride, potassium, bicarbonate, Bun, Creatine, magnesium, pro BNP)
- Dyspnea scale (appendix B)
- Assessment for adverse events
- Assessment for interval hospitalizations, ED visits, or unscheduled clinic visits

At this visit, the physician can decide if the treatment should be extended for four extra days (after the initial three days of therapy). If there is no interval improvement, the physician can withdraw the subjects from the trial for safety reasons. The initial follow up assessment will be included in the final analysis. Patients who show improvement with initial treatment (3 days or 3 day plus up to 4 days at home) may be offered 3 extra days of “rescue treatment” as needed within 30 days of enrollment in the trial. During the “rescue treatment” they will be evaluated daily by the visiting nurse and at follow up if they need further assessment as done during the treatment phase.

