	
experience and results and consider any adjustments to the study or workflow before commencing the Evaluation Phase of the study in which an additional 40 patients will be recruited. The Evaluation Phase may involve participation by other Steward Health Care System hospitals. Adjustments to the study procedures are subject to IRB review and approval.
 
Participants will be treated daily for 3 consecutive days at home after an assessment in the cardiology clinic. Patients will be homebound during the episode of care for decompensated heart failure. Patients will be visited daily by Steward Home Care and Hospice for home health nursing services. In the evening, participants will have the opportunity to supplement diuresis with their usual oral diuretic dose.
 
Patients will be evaluated by a cardiologist at SEMC within 24 hours after the 3rd dose of sc2Wear furosemide. If a patient was found to have satisfactorily responded but requires additional parenteral diuretics an additional 4 days may be prescribed for a total of 7 consecutive treatments.
 
Additionally, up to three sc2Wear furosemide at home treatments may be used as authorized by the treating physician in case the patient experience worsening of heart failure from day 7 to up to 30-days after enrollment.
 
Response will be based on the weight loss, decrease in pro-BNP, or improvement in the dyspnea scale. If additional units are prescribed, patients will be re-evaluated by a cardiologist within 24 hours after the last dose of sc2Wear furosemide. Participants will require a final follow up with a cardiologist at 30-33 days after the start of the study for a post treatment interview and assessment.
 
The protocol is subject to IRB review and approval. The study will be conducted under an Investigator-Initiated Investigational New Drug (IND) Application.

STUDY PROCEDURES	
Screening Phase:
 
The cardiology service will screen patients with mild to moderate fluid overload. Patients who present with other serious or life threatening condition for which hospitalization would be indicated are excluded. Women of child bearing potential will be screened for pregnancy with a urine pregnancy

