	
 • Body Weight • Vital signs • HF Physical examination • Dyspnea scale • Routine laboratory panel (incl. electrolyte, pro-BNP) • Adverse events • Injection site assessment 
Participants will visit the clinic 30 ± 3 days after the start of the study for a post treatment evaluation.
 
Evaluation Phase
 
The Evaluation Phase mirrors the Pilot Phase except that attempts will be made to test pre-defined clinical care paths based on the lessons of the Pilot Phase. Up to two additional Steward Health Care sites may participate in the Evaluation Phase.

SC2WEAR TREATMENT	
Novel Furosemide Injection formulation at neutral pH, 8 mg/mL, (total dose =80 mg) administered subcutaneously by means of the sc2Wear Infusor as 30 mg over the first hour and then as 12.5 mg per hour over the subsequent 4 hours.
 
Participants will be treated for 3 sequential days with one dose of sc2Wear Furosemide Infusor (80mg) daily. It is generally recommended that the sc2Wear infusor be applied in the morning. Oral diuretics should be continued concomitantly
 
If a patient was found to have satisfactorily responded but requires additional parenteral diuretics an additional 4 days may be prescribed for a total of 7 consecutive treatments.
 
Additionally, up to three sc2Wear furosemide at home treatments may be used as authorized by the treating physician in case the patient experience worsening of heart failure from day 7 to up to 30-days after enrollment.
 
(Rescue Treatment).

NUMBER OF SUBJECTS	60 (20 in Pilot Phase, 40 in Evaluation Phase)
NUMBER OF SITES	Pilot Phase: St Elizabeth's Medical Center Evaluation Phase: Up to three hospitals in the Steward Health Care System
PARTICIPATING COUNTRIES	U.S.
SUBJECT POPULATION	Male and female patients over the age of 18 with mild to moderately decompensated heart failure not requiring hospital admission for care. Subjects may be enrolled in the study only if all inclusion criteria and none of the exclusion criteria are met.

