Additionally, up to three-sc2Wear furosemide at home treatments may be used as authorized by the treating physician in case the patient experience worsening of heart failure within 30-days of enrollment (Rescue Treatment). Participants will be seen in clinic for follow up at 30 ± 3 days after the start of the study for a post treatment follow up. A Time and Events Schedule is attached as **Appendix A**.

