9.4 Day 30 ± 3 Clinic Visit

At Day 30, study follow-up (+/- 3 days). Subjects will undergo the following assessment.

- Medical history
- Physical examination
- Weight, Blood pressure, Heart Rate, Respiratory Rate, Temperature
- NYHA classification

- Injection site inspection
- Blood draw (sodium, potassium, chloride, bicarbonate, Bun, Creatine, magnesium, pro-BNP)
- Current Medications
- Assessment for interval hospitalizations, ED visits, or unscheduled clinic visits
- Assessment for adverse events
- Dyspnea Scale (Appendix B)

Visiting Nursing Timeline

A week prior to the initiating of the study, the visiting nurses will be given an orientation and will be taught how to use the sc2Wear Furosemide Infusor. They will also be trained on how to use the dyspnea scale to ensure consistency of the results.

The visiting nurse will visit the participant at home within 24 hours of starting the treatment. These visits will occur on the three treatment days and an additional 4 days if it is determined that the participant needs extra days. Also participants who need an extra three days of rescue treatment during 30 days will be seen on consecutive days by the visiting nurse.

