19 APPENDICES

Appendix A. Schedule of Assessments

	Screening	Baseline	Treatment*	First Post Treatment	Second Post Treatment (if applicable)	Post-Treatment Visit
Day	0	0	Daily (3 ± 4 days)	Within 24hrs of last treatment	Within 24hrs of last treatment	30±3days after first dose
Informed Consent	X					
Pregnancy Test*	X					
Training		X				
Medical History		X				
Initial sc2Wear Treatment		X				
Weight		X	X	X	X	X
Height		X				
HF Physical Exam		X	X	X	X	X
NYHA		X		X	X	X
Baseline Labs ^a		X				
Monitoring labs ^b			X	X	X	X
Vitals Signs ^c		X	X	X	X	X
Dyspnea Scale		X	X	X	X	X
Electrolyte correction		X	X			
Injection Site Inspection			X	X	X	X
Current Medication	X	X	X	X	X	X
Adverse Events ^d		X	X	X	X	X

- * To be performed by Steward Home Care and Hospice in accordance with standard practices for homebound heart failure patients
- a. Baseline laboratory panel (Sodium, potassium, Bun, Cr, Mg, pro-BNP, Hemoglobin and Hematocrit)
- b. Monitoring laboratory panel: (sodium, chloride, bicarbonate, potassium, Bun, Cr, Mg)
- c. Vital signs: Blood pressure, heart rate, temperature, respiratory rate
- d. Adverse Events: Major Event: death, hospitalization, MACE (major adverse cardiac event); Minor: ER visit for acute decompensated heart failure (excluding study related visits), admission to SNF or similar inpatient facility

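### The final-visit window is stated two ways, and under 30 ± 3 a compliant visit on day 27, 28 or 29 comes before the end of the 30-day endpoints and the last day for rescue, with no later contact scheduled

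*Combined protocol and SAP*

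**What the plan says.** **Final visit.** The synopsis, under Study Design & Duration, says "Participants will require a final follow up with a cardiologist at 30-33 days after the start of the study". Section 5 says "Participants will be seen in clinic for follow up at 30 ± 3 days after the start of the study". Section 9.4 says "At Day 30, study follow-up (+/- 3 days). Subjects will undergo the following assessment", and Appendix A has "30±3days after first dose". The synopsis Study Procedures text also uses 30 ± 3, so the synopsis disagrees with itself.

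**Rescue.** The synopsis allows up to three further doses "in case the patient experience worsening of heart failure from day 7 to up to 30-days after enrollment". Section 9.3 offers three extra days "as needed within 30 days of enrollment in the trial".

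**Assessment after dosing.** Section 9.3 opens with a general rule: "Subjects will be assessed in the office within 24 hours of termination of at home treatment". Later in the same section, the sentence specific to rescue reads "they will be evaluated daily by the visiting nurse and at follow up if they need further assessment as done during the treatment phase". Appendix A has no column for rescue.

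**Endpoints.** Section 10.1 measures survival, freedom from heart-failure hospitalization and freedom from significant heart-failure events, all to 30 days after enrollment. Section 14 counts re-admission and 30-day survival among the primary endpoints. Section 9.4 makes the day-30 visit the last scheduled occasion for asking about interval hospitalizations, ED visits and unscheduled clinic visits.

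**The concern.** A site following section 9.4 or Appendix A can hold the last visit up to three days before the endpoint period closes. On that day nobody can establish that the patient was alive and out of hospital on day 30. This applies to every patient, rescued or not.

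The same early visit can also precede rescue doses that the protocol still permits. If the 24-hour office assessment were read as not covering rescue, a late course could finish without an assured clinic and laboratory check after its last dose. Magnesium and creatinine matter here because section 13.5 uses them to define pre-specified adverse events, whereas the 24-hour monitoring trigger in section 9.5 concerns potassium only.

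**Working it through.** The plan gives no figure for this point. Its one sample-size figure, 59 evaluable patients in section 14, reproduces (1 − 0.95^59 = 0.9515; 58 patients give 0.9490) and does not bear on the visit window.

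**Inputs.** Enrollment and first dose are both day 0 (Appendix A; the synopsis has the first infusor activated on arrival home). The visit window is days 27-33 (30 ± 3) or days 30-33. Endpoints close on day 30. Rescue runs from day 7 to day 30, with up to three doses. There are 60 patients. No rescue rate is given.

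**Step 1: endpoint days after the visit.** Days remaining = 30 − visit day.

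- Day 27: 3 days, or 3/30 = 10% of the period.
- Day 28: 2 days, or 6.7%.
- Day 29: 1 day, or 3.3%.
- Days 30-33: none.

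So 3 of the 7 visit days under 30 ± 3 fall short, against 0 of 4 under 30-33. If the first dose came one day after enrollment and the visit were counted from first dose, only enrollment days 28 and 29 would fall short.

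**Step 2: expected first events after the visit.** Assume a constant hazard, so S(t) = (1 − p)^(t/30), with p the 30-day event rate. The range p = 10% to 25% is an assumption. The upper value is the 30-day readmission figure quoted in section 3.1. Expected number of 60 = 60 × [S(v) − S(30)].

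| Visit day v | p = 10% | p = 25% |
|---|---|---|
| 27 | 60 × (0.9095 − 0.9000) = 0.57 | 60 × (0.7719 − 0.7500) = 1.31 |
| 28 | 60 × (0.9063 − 0.9000) = 0.38 | 60 × (0.7645 − 0.7500) = 0.87 |
| 29 | 60 × (0.9032 − 0.9000) = 0.19 | 60 × (0.7572 − 0.7500) = 0.43 |
| 30-33 | 0 | 0 |

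With visits spread evenly over the seven days, the averages are (0.57 + 0.38 + 0.19)/7 = 0.16 and (1.31 + 0.87 + 0.43)/7 = 0.37 patients.

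**Step 3: rescue doses after the visit.** A three-day course starting on day s has its last dose on day e = s + 2.

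- *All doses end by day 30* (s = 7 to 28, 22 start days). Visits on days 27, 28 and 29 precede the last dose for 3, 2 and 1 start days: 6 of 22 × 7 = 154 start-day/visit-day pairs (3.9%). Under days 30-33 there are none.
- *A course may start as late as day 30* (s = 7 to 30, 24 start days, e up to 32). Visits on days 27 to 31 precede the last dose for 5, 4, 3, 2 and 1 start days: 15 of 24 × 7 = 168 pairs (8.9%). Under days 30-33, visits on days 30 and 31 still do.

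These pair counts describe the calendar. They are not probabilities and concern rescued patients only.

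**Step 4: holding the visit.** If a known course is completed first and the visit is held the day after the last dose, the latest day needed is 31 on the first reading and 33 on the second, inside both windows. This works only when rescue is known about before the visit. A single dose given later on day 30, after a completed day-30 visit, still follows the visit.

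**The case against.** **Are later events lost?** A reader might infer that deaths and hospitalizations after an early visit go unrecorded. The documents do not support that. Section 13.9 makes any adverse event reportable for 30 days after study completion, and footnote d of Appendix A lists death and hospitalization as major events and ER visits for decompensation as minor ones. Section 6.3 requires 30-day monitoring even of withdrawn patients. The narrower definition of a serious hospitalization in section 13.2 does not limit this, because section 13.9 covers all adverse events. What remains is that section 13.9 places the questioning at follow-up or nurse visits, and none is scheduled after an early final visit.

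**Are rescued patients left without a post-dose check?** This too would go beyond the text. The synopsis and section 5 describe rescue doses as treatments given at home, so the opening rule of section 9.3 can naturally be read to include them. In the synopsis, the 24-hour sentence on additional units follows the rescue paragraph. Daily nurse visits, treatment-day blood draws, the potassium trigger and discretionary interim visits also apply. What stands is that the rescue-specific sentence is conditional, and that the synopsis Study Procedures and section 5 attach the additional-units rule to the four-day extension.

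**Can rescue run to day 32?** The synopsis can be read that way, because it dates the worsening and not the doses. Section 9.3 and the nursing timeline in section 9.4 favour treatment days ending by day 30, so the larger rescue counts rest on the weaker reading.

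**Is the effect small?** Yes. With visits spread evenly it is 0.16/60 to 0.37/60, or 0.3 to 0.6 percentage points, in a descriptive study with no hypothesis test.

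**Conclusion.** The inconsistency in the visit window is real. Under 30 ± 3, a patient can comply fully and have no scheduled contact covering the last one to three days of the 30-day endpoints or the last days on which rescue is permitted. The shortfall is in active ascertainment; the duty to report events is already there.

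The size is about 0.2-0.4 of 60 patients with visits spread evenly over days 27-33, and at most 0.6-1.3 if every visit were on day 27. These figures assume a constant hazard and a 10%-25% event rate, and count every event after the visit whether or not spontaneous reporting would capture it. The upper rate comes from a readmission statistic, whereas this trial enrolls patients not needing admission. The number of rescued patients affected cannot be estimated.

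A reader might also infer that holding the final visit until after rescue closes the gap completely. It does not, since rescue can begin at or after a completed visit. The point is minor. The scope of the 24-hour rule is a clarification that would not merit a separate point.

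**What to change.** 1. Use the day 30-33 window already in the synopsis (Study Design & Duration) in the synopsis Study Procedures, section 5, section 9.4 and Appendix A.
2. State in sections 9.3 and 9.4 that the final visit is held until after the last dose of any rescue course under way or planned.
3. State in section 9.3 that the existing office assessment within 24 hours of the last dose covers rescue, so that it applies when rescue starts at or after the final visit.

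This is a wording amendment. The scheduling window shrinks from 7 days to 4, with no room on the early side, so some visits will need rescheduling. A patient rescued at or after the final visit may need one further office visit. A telephone contact on or after day 30 could close the endpoint gap without narrowing the window, but the conflicting window statements would still have to be reconciled.

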9.4 Day 30 ± 3 Clinic Visit

At Day 30, study follow-up (+/- 3 days). Subjects will undergo the following assessment.

- Medical history
- Physical examination
- Weight, Blood pressure, Heart Rate, Respiratory Rate, Temperature
- NYHA classification

- Injection site inspection
- Blood draw (sodium, potassium, chloride, bicarbonate, Bun, Creatine, magnesium, pro-BNP)
- Current Medications
- Assessment for interval hospitalizations, ED visits, or unscheduled clinic visits
- Assessment for adverse events
- Dyspnea Scale (Appendix B)

Visiting Nursing Timeline

A week prior to the initiating of the study, the visiting nurses will be given an orientation and will be taught how to use the sc2Wear Furosemide Infusor. They will also be trained on how to use the dyspnea scale to ensure consistency of the results.

The visiting nurse will visit the participant at home within 24 hours of starting the treatment. These visits will occur on the three treatment days and an additional 4 days if it is determined that the participant needs extra days. Also participants who need an extra three days of rescue treatment during 30 days will be seen on consecutive days by the visiting nurse.

